Purpose:	To confirm long-term safety and reliability of BIOTRONIK's Protego DF4 lead, as used in conjunction with a BIOTRONIK DF4 compatible implantable cardioverter defibrillator (ICD) or cardiac resynchronization therapy defibrillator (CRT-D) pulse generator. The evaluation of safety will be based on the analysis of Protego lead related adverse events. The Protego DF4 registry will provide data to permit characterization of any Protego lead failures contributing to loss of bradycardia or shock therapy. Additionally, acute and chronic Protego lead parameters will be evaluated.
Subject Population:	Subjects who are indicated for an ICD or a CRT-D. Subjects must be successfully implanted with a BIOTRONIK Ilesto DF4 ICD or CRT-D or future market released BIOTRONIK DF4 ICD or CRT-D. Enrollment can be up to 30 days prior to or 30 days after implant with the DF4 system.
Enrollment:	This registry will include 1,694 subjects implanted with the Protego DF4 system. The collection of data will continue for 5 years post-implant for each enrolled subject.
Clinical Sites:	Up to 75 U.S. and International sites.
Primary Endpoints:	
 1. Evaluation of the overall incidence of adverse events (AEs) related to the Protego lead or device header 2. Evaluation of the incidence of each individual type of AE that contributes to Primary Endpoint 1
Secondary Endpoint:	
 1. Pacing threshold, sensing and impedance measurements for the Protego lead through 5 years post-implant 2. Shock impedance for the Protego lead through 5 years post-implant 3. AE rates for AEs excluded from primary safety endpoints 1 and 2, through 5 years post-implant
Clinical Events Committee Chair:	TBD
Sponsor:	BIOTRONIK, Inc. Clinical Studies Department [name]

1. INTRODUCTION

1.1 NAME OF DEVICE

This protocol details the FDA post-approval registry for BIOTRONIK's Protego DF4 implantable cardioverter defibrillator (ICD) lead, further referred to as the Protego lead throughout this document. Currently this includes the following models: Protego SD (active fixation, dual coil), Protego TD (passive fixation, dual coil), Protego S (active fixation, single coil), and Protego T (passive fixation, single coil). Under this protocol, the Protego lead is utilized in conjunction with any market-released BIOTRONIK Ilesto or future US market released ICD or cardiac resynchronization therapy defibrillator (CRT-D) device with a DF4 header.

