1.4.3 DF4 Device Header Description

The DF4 connector features a single connection between the ICD/CRT-D and the ICD lead. As a result, the number of connectors for ICD leads is reduced from two or three connectors for a single shock coil or a dual shock coil DF-1/IS-1 ICD lead (see Figure 4 and Figure 6), respectively, to a single connection with a DF4 ICD lead (see Figure 5 and Figure 7).

Figure 4: Linx^{smart} SD Schematic

[figure not shown]

Figure 5: Protego SD Schematic

[figure not shown]

Figure 6: Orientation of DF-1/IS-1 llesto Headers

[figure not shown]
[figure not shown]

Figure 7: Orientation of DF4/IS-1 llesto Headers

VR – Single Chamber Device, DR – Dual Chamber Device, HF – Triple Chamber Device

Due to these modifications, DF4 systems require a more complex design of the generator connector cavity. Three of the four setscrews that are necessary for a dual coil DF-1/IS-1 shock lead have been replaced by spring contacts. Additionally, strict requirements are put on the seals that have to prevent leaking current as well as prevent liquid from entering the header cavity. Conformity with this standard ensures that the DF4 generator connector can be connected to any DF4-labelled lead. For purposes of the Protego DF4 post-approval registry, the BIOTRONIK Protego ICD lead is required.

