2.1.4 Additional Data of Interest

Additional information will be collected to characterize the registry population, implanted system, and progress of the registry. The collected information will include baseline demographics, medical history, implanted system, system revisions, Protego extractions, returned product analysis, and compliance. Specifically, data of interest will include:

- Baseline demographics, including age, gender, weight, height, New York Heart Association (NYHA) class, ejection fraction, and race and ethnicity (optional)
- Medical history, including indication for device
- Implanted device data, including pulse generator and leads models, serial numbers, and implant dates from initial implant and/or revisions
- Implant procedure data (collected retrospectively if implant occurred prior to enrollment)
- Pacing threshold, sensing and impedance measurements for implanted BIOTRONIK RA and LV leads
- Site reported adverse events excluded from primary and secondary endpoint analysis
- Protego DF4 extraction experience
- Results from returned product analysis
- Compliance to protocol requirements and registry visit schedule

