2.3 SAMPLE SIZE ANALYSIS

The estimated sample sizes required to evaluate primary endpoints 1 and 2 are based on a superiority comparison of the overall Protego DF4 lead AE free-rate to 92.5% at 5 years, and a non-powered, superiority comparison for those individual lead-related AEs to 1% at 5 years. The sample size for primary safety endpoint 1 was calculated based on the following assumptions:

Assumptions for primary safety endpoint 1

- Study Design: nonrandomized registry
- Test basis: exact binomial test
- Type I error (alpha): 0.025 (one-sided for superiority)
- Statistical power: 80%
- Estimated AE-Free Rate at 5 years: 95.0% for Protego Leads
- Performance goal for AE-Free Rate at 5 years: 92.5%

For primary safety endpoint 1, a total of 750 evaluable Protego leads would be required to demonstrate superiority to an AE free-rate of 92.5% (see Table 3). Assuming a 10% loss to follow-up rate per year over 5 years of follow-up (average of 8.2% of original population per year), a total of 1271 ($=750/0.9^5$) subjects with an ICD lead would be required to be enrolled to evaluate primary safety endpoint 1.

Assumptions for primary safety endpoint 2

- Estimated individual AE rate at 5 years: 0.4%
- Allowable two-sided, upper 95% confidence bound: 1%

For primary safety endpoint 2, a total of 1000 evaluable subjects with Protego DF4 leads would be required to demonstrate a two-sided, upper 95% confidence bound of 1%, assuming an expected individual AE rate of 0.4% (see Table 3). Assuming a 10% loss to follow-up rate per year over 5 years of follow-up (average of 8.2% of original population per year), a total of 1694 ($=1000/0.9^5$) subjects would be required for evaluation of primary safety endpoint 2.

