2.4.4 Poolability Analysis

The distribution in AE free-rates across centers will be examined. The significance of differences in rates between centers will be initially tested using a Kruskal-Wallis test statistic, with an associated p-value of 0.15 or less considered evidence of center differences.

A Cochran-Mantel-Haenszel test with continuity adjustment will be used to assess the poolability of data collected across the different centers. If evidence is found of center differences, then the reasons for the differences will be explored using Cox and logistic regression methods to determine if any baseline subject risk factors are explanatory.

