10.1.2 Pulse Generator-Related Adverse Events

An AE will be classified as pulse generator-related if any one of the following occurred:

- DF4 header connector malfunction
- DF4 header fluid intrusion
- Device migration
- Premature battery depletion
- Pulse generator failure
- Skin erosion

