10.3 ADVERSE EVENTS FOR THE ANALYSIS OF THE PRIMARY AND SECONDARY ENDPOINTS

10.3.1 Adverse Events for the Analysis of Primary Endpoints 1 and 2

If any of the following invasive actions occur in order to resolve an above listed Protego lead-related AE, the AE will be included in the primary safety endpoint analysis:

- Lead surgically repositioned
- Lead surgically explanted
- Lead surgically replaced
- Lead surgically abandoned
- Other lead-related surgery performed

Additionally, if any of the following non-invasive actions occur in order to resolve an above listed Protego lead-related AE, the Protego lead-related AE will be included in the primary endpoint analysis:

- Lead pacing polarity or pacing mode reprogrammed due to suspected lead failure.
- Lead abandoned and pacing disabled due to clinical failure or suspected lead failure
- Lead use continued based on medical judgment despite a known clinical failure or suspected lead failure

AEs that are corrected by reprogramming the pulse generator (other than the above) and resolved without invasive action will not be considered an adverse event counted towards the primary endpoints. For example, electrical reprogramming of the pacing polarity to eliminate extra-cardiac stimulation will not be considered an adverse event. Similarly, increasing pacing output as a result of an elevated threshold without further intervention does not count toward the primary endpoint analysis.

Subject deaths as a result of a Protego lead-related AE will be included in the primary endpoint analysis.

Primary endpoints 1 and 2 will exclude 1) lead dislodgements that occur within 30 days after lead implant or a lead revision procedure and 2) high pacing threshold, intermittent capture, no lead capture within 30 days after lead implant or a lead revision procedure. However, these will count towards the adverse event secondary endpoint.

In addition, the following two pulse generator-related adverse events will be included in the analysis of primary endpoints 1 and 2: DF4 header connector malfunction and DF4 header fluid intrusion.

10.3.2 Adverse Events for the Analysis of Secondary Endpoint 3

If any of the following invasive actions occur in order to resolve an above listed RA or LV lead-related AE, the AE will be included in the secondary endpoint analysis:

- Lead surgically repositioned
- Lead surgically explanted
- Lead surgically replaced
- Lead surgically abandoned
- Other lead-related surgery performed

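### The two DF4 header event types are analysed only pooled over all generators; a descriptive table by generator family is a cheap addition

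*Combined protocol and SAP*

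**What the plan says.** - **Where the risk sits.** Section 1.4.3 states that "DF4 systems require a more complex design of the generator connector cavity". Section 10.1.2 lists DF4 header connector malfunction and DF4 header fluid intrusion under the rule "An AE will be classified as pulse generator-related if any one of the following occurred".
- **Where they count.** Section 10.3.1 adds that "the following two pulse generator-related adverse events will be included in the analysis of primary endpoints 1 and 2", and names those same two.
- **Which generators.** Section 1.1 allows "any market-released BIOTRONIK Ilesto or future US market released ICD or cardiac resynchronization therapy defibrillator (CRT-D) device with a DF4 header". No minimum or maximum per family is set. Appendix B plans enrollment from December 2014 to May 2019.
- **Analysis.** Section 2.4 uses one ITT population. Section 2.4.1 tests each event type against 1% with an exact two-sided 95% interval. The only planned heterogeneity check is by center: "The distribution in AE free-rates across centers will be examined" (2.4.4).
- **Trigger.** Section 2.4.2 requires a summary to FDA if survival falls, or is projected to fall, below 92.5% overall or 99% for an event type. There is no split by generator.
- **Clock.** Section 2.1.1 counts from implant, and section 5.2 sets visits from the Protego lead implant date. Section 3.3.3 withdraws a subject after a generator change only when the new device is not from the sponsor. No rule restarts or censors header time at replacement.
- **Data available.** Section 2.1.4 collects "Implanted device data, including pulse generator and leads models, serial numbers, and implant dates from initial implant and/or revisions".

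**The concern.** A header failure is a property of the generator, and the generator is the component that the plan leaves open to change over an enrollment period of more than four years. A pooled rate answers whether header failures are rare across the mix of generators that sites happened to implant. It does not show whether they are rare for each family in that mix.

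The clock adds a smaller problem. A subject who receives a second DF4 generator from the sponsor can stay in the registry, and the second header's shorter exposure then counts as part of a 5-year header result.

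At stake is how informative the final and interval reports are about the header. As planned, a reader would see a pooled header rate and individual failure investigations, but could not tell how many subjects were exposed to the generator involved.

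**Working it through.** **1. The plan's own figures.** Section 2.3 gives 750 evaluable subjects for endpoint 1, with "Type I error (alpha): 0.025 (one-sided for superiority") and "Statistical power: 80"%, and 1000 for endpoint 2.
- Endpoint 1, exact binomial, 92.5% against 95.0%: at n = 750 the test passes with at most 42 failures; alpha 0.0247, power 80.1%. Reproduced.
- Attrition: 750/0.9^5 = 1270.1 and 1000/0.9^5 = 1693.5, matching 1271 and 1694.
- Endpoint 2, Clopper-Pearson upper bound at n = 1000: 3 events give 0.874% (pass); 4 events give 1.021% (just over 1%). A type therefore passes with at most 3 events.

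**2. What a pooled pass can contain.** The documents give no family shares, so a range is assumed. If all 3 permitted events fall in one family:

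| Assumed share of 1000 | Family result | Exact 95% CI |
|---|---|---|
| 5% | 3/50 = 6.0% | 1.25 to 16.5% |
| 10% | 3/100 = 3.0% | 0.62 to 8.52% |
| 20% | 3/200 = 1.5% | 0.31 to 4.32% |
| 30% | 3/300 = 1.0% | 0.21 to 2.89% |

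**3. Chance of a pooled pass.** This is P(X ≤ 3), X ~ Bin(family size, true family rate), with no events in other families:

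| Share | True rate 2% | True rate 3% |
|---|---|---|
| 5% | 98% | 94% |
| 10% | 86% | 65% |
| 20% | 43% | 15% |
| 30% | 15% | 2% |

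A background rate of 0.1% elsewhere (also assumed) lowers the 65% to 45%. The effect belongs to small families and is nearly gone at a 30% share with a 3% rate.

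**4. Can a pooled pass coexist with a family demonstrably above 1%?** At n = 1000, a family of 100 needs 4 events (lower bound 1.10%) and a family of 200 needs 6 (1.11%) before its own exact lower bound exceeds 1%. Either count already fails the pooled test. Three events suffice only in a family of 62 or fewer (3/62: 1.01%; 3/63: 0.99%). If attrition is below the assumed maximum, the limit loosens: 5/1200 passes (upper bound 0.97%), while 5/120 in one family has a lower bound of 1.37%.

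**5. The pooled 99% trigger.** As simple proportions without censoring, 9 events in a family of 100 is 9% (exact lower bound 4.2%). Pooled, it is 9/1000, so survival is 99.1%, above the threshold. More generally, with no events elsewhere, the observed family rate must exceed 1%/0.10 = 10% at a 10% share, or 1%/0.20 = 5% at a 20% share, before pooled survival falls below 99%. This concerns observed survival; the projected limb of the rule could act sooner. At 5 years 9/1000 would fail the endpoint 2 test (upper bound 1.70%), so the insensitivity is in the ongoing monitoring.

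**6. Relatedness.** Section 10.2 counts only events adjudicated as related, and the relatedness it defines is to the Protego lead. Section 10.3.1 includes two generator events. Read literally, a pure header fault could be judged unrelated to the lead and drop out of the endpoints that 10.3.1 puts it in.

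**The case against.** The strongest case against is that nothing is concealed. Section 2.4.2 investigates the root cause of any failure whatever its rate, and has a second route with no threshold: one failure, or a combination of events, believed to affect safety goes to FDA. Returned product analysis is collected. Each header type is tested separately, so lead events do not dilute it. This stands. A reader might infer from the pooling that a faulty header design can hide behind a pass; the documents do not support that. What these safeguards lack is a denominator.

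A reader might also infer that the registry could pass while one family is clearly above 1%. At 1000 evaluable subjects and shares of 10 to 20%, step 4 shows that it cannot, in the sense of an exact lower bound above 1%. The exceptions are very small families or a larger evaluable sample.

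Nor do the documents show that header designs differ between generators. DF4 is a standard connection, and section 1.4.3 refers to conformity. That conformity is stated to ensure connection with DF4-labelled leads; it does not establish equal failure rates. The difference is therefore unknown, and generator family is only a proxy for header design.

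On the clock, header and lead usually start together, no replacement frequency is given, and a failure of the first header before replacement still counts. The point is real but of unknown size.

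Finally, section 2.4 already promises cross tabulations for discrete variables, so such a table could be produced. It does not name this one, the exposure count or the time origin.

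**Conclusion.** This is a cheap improvement, not a flaw in the primary tests. The two header event types are generator events that 10.3.1 counts in both primary endpoints, and the plan gives no rate or denominator for them by generator family or from the generator's own implant date.

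The consequence depends on family size. If a family holds about 10% of 1000 evaluable subjects with a true 3% rate and no events occur elsewhere, the pooled test passes 65% of the time; at a 30% share it passes 2% of the time. The pooled 99% threshold can stay uncrossed with 9 events in a family of 100. These figures rest on assumed shares and assumed rates elsewhere.

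The pooled hypotheses remain valid for the question they ask. The need to reconcile 10.2 with 10.3.1 does not depend on any of these assumptions.

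**What to change.** Keep the pooled tests, the sample size and the pooled trigger unchanged.

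1. In 2.4.1 and in the interval reports under 2.4.2, add a table, labelled descriptive, of the two header event types by generator family: number exposed, events and exact 95% CI.
2. Add Kaplan-Meier estimates for these two types, timed from that generator's implant and censored at its replacement.
3. Reconcile 10.2 with 10.3.1 by stating how relatedness is judged for header events, so that they are not dropped.

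Do not add a per-family 99% trigger. One event would cross it in any family under 100 (1/99 is already above 1%), and at the plan's expected 0.4% rate a family of 50 would cross it with probability 1 − 0.996^50 = 18% per event type. Do not add a formal poolability test by family either; a handful of events cannot support it. A separate 1% test per family is also unrealistic, since a family would need at least 368 evaluable subjects with no events to pass.

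The cost is a few sentences and some tables from data already collected. The downside is wide intervals and possible chance findings in small families, hence the descriptive label.

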1.2 REGISTRY OVERVIEW

The purpose of this post-approval registry is to confirm the safety and reliability of the Protego lead as used in conjunction with any compatible BIOTRONIK Ilesto or future US market released DF4 ICD or CRT-D device. Data will be collected from up to 1694 subjects from implant through 5 years of follow-up.

Subjects eligible for the registry include those that will be implanted with a Protego lead within the 30 days following enrollment procedures or have been implanted with a Protego lead within 30 days of enrollment. Prior to enrollment procedures, subjects will be screened to ensure eligibility and will sign an informed consent. Consent and enrollment must occur at a maximum of 30 days prior to or post implant of the Protego lead.

Safety will be evaluated based on the analysis of all Protego lead and device header-related adverse events. Acute and chronic lead parameters for sensing, pacing thresholds, and pacing and shock impedance will be evaluated for the Protego lead. Additionally, acute and chronic lead parameters for sensing, pacing thresholds, and pacing impedance will be evaluated for all BIOTRONIK leads, including right atrial and left ventricular leads.

All devices included in the registry are legally marketed and prescribed by physicians according to approved indications for use.

1.3 BACKGROUND

The Protego DF4 Post-Approval Registry is designed to document the clinical experience of the Protego leads as required by the FDA through P980023/S057, dated July 3, 2014.

The term DF4 refers to an industry standard header/lead connection scheme between an ICD/CRT-D device and the ICD lead. The DF4 header/lead system features a single connection between the ICD/CRT-D device and the ICD lead. As a result, the number of connectors for an ICD lead is reduced with a DF4 header/lead system compared to a

DF-1/IS-1 system, which simplifies the implantation procedure, reduces the likelihood of lead-to-port mismatch, and decreases the number of setscrews necessary to secure the lead into the header. Section 1.4.2 provides further details on differences between the DF4 and DF-1/IS-1 connection schemes. Additionally, by eliminating the lead yoke, the system pocket bulk can be reduced.

The Protego lead is a 7.8 French transvenous ICD lead designed for permanent right ventricular pacing, sensing, and delivery of defibrillation/cardioversion shocks to the heart. Protego is the successor of the Linx^{smart} ICD lead (Linx^{smart} SD/TD P980023/S038, approved September 17, 2010, Linx^{smart} S/T P980023/S043, approved February 28, 2011), the only major difference being the replacement of the traditional DF-1/IS-1 connectors of the Linx^{smart} lead with the DF4 connector. The Linx lead family has been extensively studied in the ongoing GALAXY registry.

1.3.1 GALAXY Lead Registry: Clinical Experience with Linx ICD Lead

BIOTRONIK is currently conducting GALAXY, an after-market registry to confirm the long-term safety and reliability of the FDA approved Linx family of ICD leads. The GALAXY Registry is registered on clinicaltrials.gov, NCT00836589. This multi-center, prospective, non-randomized registry has been ongoing since enrollment began in January 2009 and has been closed to enrollment since November 2011. There were 1999 subjects enrolled in the registry, 196 of which were implanted with Linx^{smart} leads.

The sensing and pacing behavior was evaluated as well as the rate of lead related complications over the available follow-up period. The mean pacing threshold across all Linx and Linx^{smart} lead models was 0.63 ± 0.33 V. The mean sensing amplitude was 12.83 ± 5.43 mV. The mean lead impedance was 556.7 ± 124.8 ohms. There were 5 (2.55%) subjects who experienced a primary adverse event (AE) reported as related to the Linx^{smart} lead (Table 1) and 29 (1.45%) subjects who experienced a primary AE related to the Linx Lead Family.

Table 1: Linx Smart Lead Related Adverse Events

Adverse Event	Linx ^{smart} Leads (n=196)			All Linx Lead Models (N=1,999)		
	Subjects with AE, n	% Subjects with AEs	AEs, n	Subjects with AE, n	% Subjects with AEs	AEs, n
Primary Endpoint AEs						
Other ICD lead related: Lead oversensing or noise	3	1.53%	3	13	0.65%	13
Lead dislodgement > 180 days	1	0.51%	1	5	0.25%	5
Lead impedance out of range, High impedance, Potential conductor fracture	1	0.51%	1	5	0.25%	5
Lead impedance out of range, Low impedance, Potential insulation break	0	0.00%	0	5	0.25%	5
Lead undersensing or loss of sensing	0	0.00%	0	2	0.10%	2
Other ICD lead related: Tension pneumothorax	0	0.00%	0	1	0.05%	1
Total Primary Endpoint AEs	5	2.55%	5	29	1.45%	31
Secondary Endpoint AEs Related to the ICD Lead						
Lead dislodgement < 180 days	2	1.02%	2	22	1.10%	22
High pacing threshold, intermittent capture, no lead capture	0	0.00%	0	7	0.35%	7
Cardiac perforation with or without tamponade	0	0.00%	0	4	0.20%	5
Total Secondary Endpoint AEs	2	1.02%	2	33	1.65%	34
Total Primary or Secondary AEs	7	3.57%	7	60	3.00%	65

Figure 1 shows the calculated Kaplan-Meier actuarial graph demonstrating the freedom from all primary endpoint adverse events adjudicated by the Clinical Events Committee. Table 2 displays the associated case summary. A common, final follow-up date of November 4, 2013, is assumed for all active subjects.

The standard error (SE) for the estimated survival (freedom from AEs) was calculated using the method of Peto et al. The last adverse event occurred on day 1,465, and the current estimated freedom from adverse events is 97.5% (SE 1.0%) for implant times 1,465 days or longer. These estimates may change as additional follow-up data are collected.

Figure 1: Freedom from Primary Endpoint Adverse Events (%)

[figure not shown]

Table 2: Primary Endpoint Case Summary

Total Subjects, n	Subjects with Adverse Event, n	Censored	
		n	%
1999	29	1970	98.5%

